## 6.2 Patient Confidentiality

The identity of the patients participating in this study will be protected by the use of a subject number on all study materials, including specimen requisitions, laboratory reports, case report forms, etc.

## 7.0 Statistical Plan

### 7.1 Sample Size Determination

The sample size for this study is estimated to be 152 participants / group (304 total) based on the primary outcome of 60-day all cause readmission. The calculation and assumptions made are detailed below:

Assumptions:

- Standard of care 60 readmission rate: 25%. This estimate is based on the Bon Secours Richmond Health System data for December 2013 - November 2014.
- A 50% reduction in the readmission rate would be a clinically relevant difference

- Type 1 error rate: alpha=0.05 (two-sided)
- No interim analysis
- No site effect so that the data across sites could be pooled for purposes of sample size determination

A chi-square test of proportions at the alpha=0.05 level of significance will have 80% to detect the 12.5 percentage point difference (i.e., 25% vs. 12.5%) in 60 day readmission rates provided 152 participants per group are enrolled. The sample size calculations are estimated using the bsamsize function from the Hmisc package using R version 3.1.1.

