### 4.2 Randomization

Participants will be allocated to their respective treatment groups in a 4:1 ratio (intervention to standard of care), stratified by institution, sex, and NYHA functional classification. This unequal allocation ratio will lead to more patients receiving active intervention while maintaining a random component so that study staff and patients are unable to predict treatment assignment before randomization.

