An RN will be designated as the primary coach on the high touch study team focused on disease management including symptom recognition, adherence to treatment strategies, care coordination, medication matters, and problem solving. Medication matters include initial medication reconciliation and the organization of resources to obtain medications for patients who have socioeconomic challenges. A RN will also be responsible for managing socio-economic challenges, and providing a nutrition and wellness assessment and goal setting. The high touch study team establishes a patient-centric relationship using techniques of motivational interviewing coupled with a transactional model of communication. Health literacy will be assessed using a validated tool to help personalize coaching interactions. Coaching topics will include the patient's understanding of their disease, establishing goals of health, treatment strategies, medication adherence, and therapy expectations. As the high touch study team identifies knowledge deficits, they customize the education and employ the teach-back

methodology to address the gaps. The high touch study team will engage the patient in collaborative care planning and goal setting to ensure interventions are congruent with the patient's readiness for change, needs, values, culture, desires, and health goals. Patient engagement and self-care management will be measured with the Self-Care of Heart Failure Index in a pre-test/post-test fashion at the time of enrollment and at 60 days post-enrollment.

The research coordinator will screen patients hospitalized with ADHF. Those who meet all inclusion and exclusion criteria will be randomized with unequal allocation, 4:1 Tele-HC intervention to standard care and enrolled in the study. Demographic and clinical data will be collected.

All patients will be assessed at 30 days and 60 days for the occurrence of re-hospitalization and all-cause mortality. De-identified hospital records will be collected so that the study monitor can review to verify cause of re-hospitalization.

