### **5.0 Subject Selection, Enrollment and Withdrawal**

This protocol will accrue 304 subjects hospitalized with a primary or secondary diagnosis of ADHF. These subjects will then be enrolled and randomized to receive either standard care or to the intervention group (Tele-HC model) to assess the impact of the intervention on 60 day all cause readmission rates.

Definition of ADHF: One or more of these symptoms: shortness of breath, orthopnea or edema AND may have one or more of these signs: rales, peripheral edema, ascites, or pulmonary vascular congestion on chest radiography

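### The 80% power is calculated for 152 patients per group, but the trial randomizes 304 patients 4:1, which gives about 66% power for the same effect

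*Combined protocol and SAP*

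**What the plan says.** Section 7.1 (Sample Size Determination) assumes two equal groups: "The sample size for this study is estimated to be 152 participants / group (304 total"). Its inputs are a two-sided test ("Type 1 error rate: alpha=0.05 (two-sided"), a standard-care rate of 25% and a halving of that rate, with no interim analysis and no site effect. The power claim, "A chi-square test of proportions at the alpha=0.05 level of significance will have 80% to detect the 12.5 percentage point difference", is explicitly conditional: "i.e., 25% vs. 12.5%) in 60 day readmission rates provided 152 participants per group are enrolled".

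Section 4.2 (Randomization) sets a different design: "Participants will be allocated to their respective treatment groups in a 4:1 ratio (intervention to standard of care"). It gives a reason, namely that more patients receive the intervention, so the ratio is deliberate. Section 4.3, under Intervention Arm, repeats it: "randomized with unequal allocation, 4:1 Tele-HC intervention to standard care".

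The total does not change to accommodate the ratio. Section 5.0 says "This protocol will accrue 304 subjects hospitalized with a primary or secondary diagnosis of ADHF", and the Study Summary also gives 304. Section 7.1 does not mention 4:1, and no other section gives power for unequal groups.

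**The concern.** The sample size section and the randomization section describe two different trials. At a fixed total, moving from 1:1 to 4:1 lowers the precision of the comparison, because the small arm dominates the variance of the difference. Here the small arm is also the one with the higher event rate, and so the larger binomial variance per patient.

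This is the only power justification in the protocol, and it concerns the primary endpoint. If it does not apply to the trial as randomized, IRBs and readers are relying on a figure that the design lacks, and a null result would be read against a power that was never there. No interim analysis or sample size re-estimation is planned that could correct it later.

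**Working it through.** **Inputs.** From 7.1: p1 = 0.25 (standard care), p2 = 0.125 (Tele-HC), two-sided alpha 0.05 (z = 1.960), 80% power (z = 0.842). From 4.2 and 4.3: ratio 4:1. From the Study Summary, 5.0 and 7.1: total 304.

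**Formula.** Chi-square test of two proportions, pooled variance under the null, no continuity correction. With n1 standard-care and n2 Tele-HC patients and p̄ = (n1·p1 + n2·p2)/(n1 + n2):

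- S0 = √[p̄(1 − p̄)(1/n1 + 1/n2)]
- S1 = √[p1(1 − p1)/n1 + p2(1 − p2)/n2]
- power = Φ[(|p1 − p2| − 1.960·S0)/S1]

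**Step 1: reproduce the stated figure (152 and 152).**

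- p̄ = 0.1875, S0 = 0.04477, S1 = 0.04419
- (0.125 − 0.08775)/0.04419 = 0.843, so power = 80.0%
- Solving for n gives 151.87, rounded up to 152 per group

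The stated size and power reproduce, which confirms that the calculation used equal groups and this test. The continuity-corrected version would give 168 per group, and a one-sided test 120.

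**Step 2: group sizes under 4:1.** 304/5 = 60.8 standard care and 4 × 60.8 = 243.2 Tele-HC, or about 61 and 243.

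**Step 3: power with 61 and 243.**

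- p̄ = (61 × 0.25 + 243 × 0.125)/304 = 45.625/304 = 0.1501
- S0 = 0.05115, so 1.960·S0 = 0.10025
- S1 = √(0.1875/61 + 0.109375/243) = √(0.003074 + 0.000450) = 0.05936
- (0.125 − 0.10025)/0.05936 = 0.417, so power = 66.2%

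The standard-care arm contributes 0.003074 of the 0.003524 variance, about 87%. A split of 60 and 244 gives 65.7%. Exact enumeration of the uncorrected chi-square test at 61 and 243 gives 66.1%, so the result does not depend on the normal approximation.

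**Step 4: effect detectable with 80% power at 61 and 243.** Solving the same formula for p2 gives 0.105. The relative reduction is (0.25 − 0.105)/0.25 = 58%.

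**Step 5: total needed for 80% power at 4:1.** The same formula gives 87.99 standard-care and 351.97 Tele-HC patients, so 88 + 352 = 440, which is 136 more than planned.

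**Step 6: other versions of the test at 61 and 243.**

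| Version | Power |
|---|---|
| Pooled variance, two-sided (as in 7.1) | 66.2% |
| Exact enumeration, uncorrected | 66.1% |
| Exact enumeration, continuity-corrected | 59.5% |
| Unpooled variance approximation | 55.8% |
| One-sided alpha 0.05 (contrary to 7.1) | 75.4% |

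None of them reaches 80%.

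**The case against.** The strongest reply is that the arithmetic in 7.1 is correct on its own terms and openly conditional on 152 per group, so the fault is an inconsistency between sections and not a miscalculation. That is a fair description of its origin. It does not help the claim, because the condition cannot be met under 4:1 with 304 patients.

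A second reply is that 66% is itself conditional.

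- **Event rate.** The primary endpoint in 4.6.1 counts death as well as readmission, while the 25% in 7.1 is a readmission rate. The documents give no composite rate. As an assumed range, keeping a 50% relative reduction and groups of 61 and 243, power is 56% at a control rate of 20%, 75% at 30% and 82% at 35%; it reaches 80% at about 33%. Over this range 4:1 loses about 12 to 14 points against 1:1.
- **Exclusions.** Section 7.2.6 removes patients who are not discharged alive, or who are transferred where the assignment cannot be implemented. This would lower power, by an amount the documents do not allow one to estimate.
- **Test.** The primary analysis in 7.2.3 is a Cochran-Mantel-Haenszel test by site, not the simple chi-square test. Section 7.1 assumes no site effect, and the same assumption is used here.

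These points stand as qualifications: 66% is the power under 7.1's own assumptions. None of them restores 80% at 25% versus 12.5%.

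Finally, 152 might be read as the size of the standard-care arm. At 4:1 that implies 5 × 152 = 760 patients, which contradicts the total of 304 stated in 7.1 itself.

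**Conclusion.** The concern holds. With 304 patients randomized 4:1, power for 25% versus 12.5% at two-sided alpha 0.05 is about 66%, some 14 points below the stated 80%, and the risk of missing the planned effect is about 34% instead of 20%. This rests on the rates in 7.1, complete outcome data, no exclusions after randomization, no site effect and an uncorrected test. The stated power is wrong for the trial as designed and must be corrected.

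**What to change.** In 7.1, replace the equal groups of 152 with the expected 4:1 split (about 243 Tele-HC and 61 standard care). State the power of about 66% for 25% versus 12.5%, and give the difference detectable with 80% power (25% versus about 10.5%). This changes wording only: no extra patients and no change in conduct, but a less favourable stated power.

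If the sponsor wants to keep 80% with 304 patients, the consistent alternative is 1:1 allocation in 4.2 and 4.3. That needs no extra patients, but it means changing the randomization module and giving up the aim in 4.2 of treating more patients with the intervention. Keeping both 4:1 and 80% would take about 440 patients. Under 8.1, any amendment needs approval by each institution's IRB before it is implemented. The documents do not say whether enrolment has begun; if it has, a change of ratio would also need a plan for patients already randomized 4:1.

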## 7.2 *Statistical Methods*

### 7.2.1 **Descriptive Statistics**

Univariate descriptive statistics and frequency distributions will be calculated, as appropriate for all variables. Baseline values for demographic, clinical, and outcome variables (primary and secondary) will be tabulated for the treatment groups. These analyses will help identify potential confounding variables to be used as covariates in sensitivity analyses. Distributions across subgroups used in randomization will be compared to assess whether the randomization was successful in equalizing distributions of these prognostic variables across treatment groups. Putative prognostic variables that will be investigated through these descriptive analyses include variables such as age, subject inclusion group (inclusion criteria group), and proximity to the treatment provider.

### **Handling of Missing Data**

Analyses will be conducted under intention to treat principles. All randomized subjects will be analyzed. The primary outcome (all-cause readmission within 60 days of randomization) is expected to be available for all participants through continuity of care documentation, patient/family contacts and medical record searches. Death prior to 60 days will be counted as an event (See Section 7.2.3 below). If there is loss to follow-up in the groups, the cumulative probability of readmission will be estimated using the Kaplan-Meier method as a sensitivity analysis to the primary analysis.

For the remaining outcome variables, all-available-data (for longitudinal measurements) and worst-case imputation will be considered alongside of multiple imputation to test the robustness of study findings to missing data.

### **7.2.2 Multiplicity**

To avoid spurious results due to Type I error inflation, the primary endpoint of interest has been defined a priori. Secondary outcomes will not be adjusted for multiple comparisons. There are no planned interim analyses.

### **7.2.3 Primary Outcomes**

Hypothesis: The 60-day readmission rate will be decreased with the addition of remote monitoring.

To test this hypothesis, a Cochran-Mantel-Haenszel chi-square test of proportions will be used. The stratification factor in this test will be the enrolling clinical site. The primary outcome is all cause readmission, so no adjudication is required for the primary objective. If a participant dies within 60 days of initial hospital discharge prior to any readmission, the participant will be considered as readmitted for the purpose of the primary outcome.

Intention to treat analysis will be used for the primary analysis. If there is loss to follow-up in the groups, the cumulative probability of readmission will be estimated using the Kaplan-Meier method as a sensitivity analysis to the primary analysis. Differences in the hazard rates will be tested using the stratified log-rank test. An additional sensitivity analysis will be conducted using the “per protocol” analysis set (see below), which consists of all subjects that completed the study and were adherent to monitoring.

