## Study Summary

Title	A randomized study of the effectiveness of an integrated tele-monitoring and patient-centric health coaching strategy (Tele-HC) in adult patients recently hospitalized with Acute Decompensated Heart Failure (ADHF) compared to standard care
Running Title	Tele-HC
Phase	III
Methodology	Randomized
Overall Study Duration	2 years
Subject Participation Duration	1.5 years
Objectives	To test an integrated tele-monitoring and patient-centric health coaching system to reduce hospital readmissions in HF patients.
Number of Subjects	304
Diagnosis and Main Inclusion Criteria	Diagnosis: Acute Decompensated Heart Failure (ADHF) Main inclusion criteria: Hospitalized for treatment of ADHF
Study Device	BodyGuardian® Remote Monitoring System
Duration of Exposure	60 days
Reference therapy	Standard clinical care
Statistical Methodology	The primary analysis will be a Cochran-Mantel-Haenszel Chi-square test to compare the 60-day readmission rates between the two interventions while controlling for enrolling hospital (site).

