### **7.2.4 Secondary and Exploratory Outcomes**

General considerations: The secondary and exploratory endpoints require a variety of standard analytical methods along with sophisticated analytical strategies.

For the secondary endpoint of HF-related readmission, the same analytical approach described for the primary outcome measure will be used. The time to (first) hospital readmission will be modeled using a Kaplan-Meier survival and tested using a stratified log-rank test.

[figure not shown]
For all-cause mortality, the difference in the hazard for death will be tested using a stratified log-rank test on the intention-to-treat sample.

For the exploratory outcomes involving serial measurements originating from the device, longitudinal summary statistics will also be used to condense the longitudinal data stream into meaningful summary measures (e.g., daily mean BP, incremental AUCs) prior to analysis. Longitudinal changes in weight and other continuous measures such as HR and

blood pressures will be modeled using mixed effects models that incorporate random slope and intercept effects.

When the patient is actively monitoring with a BodyGuardian® Control Unit, an activity measure is gathered every 60 seconds. This measure is gathered regardless of the signal quality of the ECG signal or bioimpedance signal quality. When monitoring for 24 hours, a subject should have 1440 samples per day. Adherence for a specific day is measured as the number of activity samples gathered divided by 1440 (expressed as a percentage). Adherence for a given monitoring period will be the number of days where the daily adherence is greater than 80% divided by the total number of days (expressed as a percentage of days monitored).

**Figure 6** Secondary & Exploratory Outcomes Illustration

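### The primary test adjusts for site but not for sex or NYHA class, the other two randomization factors: still valid, but a little power is left unused

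*Combined protocol and SAP*

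**What the plan says.** - Section 4.2 allocates patients 4:1, "stratified by institution, sex, and NYHA functional classification".
- Section 7.2.3 makes the primary test a CMH chi-square and says: "The stratification factor in this test will be the enrolling clinical site". The Study Summary agrees.
- Section 7.2.1 refers to the randomization factors as prognostic without saying how strongly: "subgroups used in randomization will be compared to assess whether the randomization was successful in equalizing distributions of these prognostic variables". On covariates it says: "These analyses will help identify potential confounding variables to be used as covariates in sensitivity analyses". No named analysis adjusts for sex or NYHA class.
- Sections 7.2.3 and 7.2.4 call the log-rank tests stratified without listing strata: "Differences in the hazard rates will be tested using the stratified log-rank test"; "For all-cause mortality, the difference in the hazard for death will be tested using a stratified log-rank test on the intention-to-treat sample".

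**The concern.** When randomization is stratified on a factor that predicts outcome, the arms are balanced on it by design. A test that leaves the factor out still counts the between-level variation as noise. Its variance is then slightly too large for the design, so it rejects a little less often than it should and loses some power.

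Two things are at stake. One is power, in a trial with about 61 controls and 46 events. The other is pre-specification, because any adjustment for sex and NYHA class now depends on covariates identified from the baseline tables.

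**Working it through.** **The plan's own figure.** Section 7.1 gives 25% vs 12.5%, two-sided alpha 0.05 and 80% power. With pooled variance and mean rate 0.1875:

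n = [1.960·√(2·0.1875·0.8125) + 0.842·√(0.25·0.75 + 0.125·0.875)]² / 0.125² = (1.082 + 0.459)² / 0.015625 ≈ 152 per group.

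This reproduces, with 80.03% power at 152 + 152.

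**What 4:1 gives.** 304/5 ≈ 61 controls and 243 on intervention. Expected events are 61·0.25 + 243·0.125 ≈ 46. The simple two-proportion power is Φ[(0.125 − 1.960·0.0511)/0.0594] ≈ 66%, where 0.0511 and 0.0594 are the pooled and unpooled standard errors.

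**Tests compared.**
- Site-only CMH, without continuity correction.
- Score test: fit a logistic model without treatment (site, sex, NYHA main effects) to get fitted risks p̂ and weights w = p̂(1 − p̂). With t for treatment and z for the covariates, U = Σt(y − p̂) and V = Σwt² − (Σwtz)′(Σwzz′)⁻¹(Σwtz). Refer ((n − p)/n)·U²/V to 3.84, where p is the number of parameters without treatment. With 8 sites and three NYHA levels, p = 1 + 7 + 1 + 2 = 11 and the factor is 293/304 = 0.964.

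**Assumed inputs (not in the plan).** Permuted blocks of 5 within site × sex × NYHA. 2, 5 or 8 equal sites, or 8 unequal with the two smallest pooled. 45% of one sex, with a sex odds ratio of 1.3 (1.0 when the NYHA odds ratio is 1). Three NYHA mixes, for example I-IV at 10/30/40/20%. A log-linear NYHA effect, with NYHA analysed as I-II, III, IV. Site effect none or log-odds SD 0.5. Marginal rates 25% vs 12.5% for power and 15% in both arms for type I error. 20,000 or 40,000 trials per cell.

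| NYHA odds ratio per class | Type I error, site-only CMH | Power change, score test minus CMH (points) |
|---|---|---|
| 1 | 4.6-5.2% | −0.2 to +0.2 |
| 1.5 | 4.5-5.0% | +0.3 to +0.8 |
| 2 | 4.2-4.9% | +0.9 to +1.9 |
| 3 | 3.9-4.6% | +2.3 to +4.1 |

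The scaled score test has type I error of 4.6-5.3% throughout. Monte Carlo standard errors are 0.04-0.18 points for the paired power differences and 0.10-0.16 for type I error.

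Example power, CMH / score, with 5 sites and four classes: 66.3/66.8% at odds ratio 1.5, 66.6/67.9% at 2, 67.2/70.9% at 3.

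**Smaller separate check** (5 sites, 3,000 trials per cell). Power was 65.7/65.9, 65.1/66.1, 65.3/66.9 and 66.2/69.5% at odds ratios 1, 1.5, 2 and 3, so the changes were +0.2, +1.0, +1.6 and +3.3 points. Type I error was 3.6-5.0% for CMH and 4.5-5.1% for the score test. The standard error at 5% is √(0.05·0.95/3000) ≈ 0.4 points, so the lower values agree with the table.

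**Why the form matters.**
- *Full cross.* Ten sites × 2 sexes × 4 classes make 80 strata, with 304/80 = 3.8 patients and 61/80 ≈ 0.8 controls each. About 12% of patients then fall in strata holding one arm only. Against site-only CMH, the fully crossed CMH changed power by 0 to +2 points with 2 sites, −2 to +1 with 5, and −2 to −5 with 10.
- *Scaling.* Without the factor (n − p)/n, and with four unmerged classes, the score test ran at 5.0-5.8% type I error, with both 5.8% values at 10 sites.
- *Merging.* With four unmerged classes at 10/30/40/20%, some class had no events in 1, 9, 24 and 54% of trials at odds ratios 1, 1.5, 2 and 3. After merging, some site or class had none in 0-5.6%.

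**The case against.** The strongest reply is that this is preference. The plan names one valid, familiar primary test, the same in both places. The benefit is about half a point at a moderate NYHA effect and nil without one, and the plan supplies no value for that effect. The variables that Section 7.2.1 names as putatively prognostic are age, inclusion group and proximity to the provider. The replacement also needs a scaling factor and merging rules, and its type I error may depend on keeping them.

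Most of that stands, which is why the point is optional. It does not remove the point. The worst simulated loss is 0.2 points, the factors are already collected, and naming them in advance ends the choice from baseline tables.

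Three stronger readings are tempting and are not supported:
- *The site-only test is invalid.* Its simulated type I error shows no meaningful excess over 5%, and it falls below 5% as NYHA class becomes more prognostic.
- *The plan keeps the one factor that it assumes has no effect.* Section 7.1 does say "No site effect so that the data across sites could be pooled for purposes of sample size determination", but only for sizing. The same two-proportion calculation includes no sex or NYHA effect either.
- *Both tests reach about 71% power.* Only the score test does, and only at the strongest NYHA effect. Site-only CMH stays near 65-68%.

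**Conclusion.** The mismatch between Section 4.2 and Section 7.2.3 is real, and its consequence is small. At 304 patients and 4:1, the site-only test is valid and at worst mildly conservative. The main-effects score test adds about 0 points of power if NYHA class is not prognostic, 0.3-1 at an odds ratio of 1.5 per class, 1-2 at 2, and 2-4 at 3. These figures rest on the assumed inputs listed above. This is a cheap improvement to consider, not a correction that the trial needs.

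A reader might infer that fuller adjustment would restore the planned 80% power. It would not. The shortfall comes from sizing for equal groups while allocating 4:1, and that conflict has to be settled separately.

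The unnamed log-rank strata are a minor gap. Site is the natural reading, but the plan does not state it.

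**What to change.** 1. In Section 7.2.3 and the Study Summary, make the primary test the score test for treatment from a logistic model with site, sex and NYHA class (as used at randomization) as main effects, scaled by (n − p)/n.
2. Set the merging rules in advance and blind to outcome, for example NYHA as I-II, III, IV, with sites of fewer than 20 patients pooled. State that the test is still used if a merged level has no events; the fitted risk there is 0 and those patients add nothing to it.
3. Keep the site-only CMH test as a sensitivity analysis. Do not use a CMH test on the full site × sex × NYHA cross.
4. Name the log-rank strata in Sections 7.2.3 and 7.2.4; site is the natural choice. If sex and NYHA class are also to be adjusted for, use a site-stratified Cox score test with them as main effects, because a log-rank test stratified on all three is itself a full cross. The time-to-event tests were not simulated here.

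Cost: no added patients, visits or data. The factors must be known before the randomization module described in Section 9.4 assigns the arm, and Section 4.4 already collects pre-discharge NYHA class in both groups. The price is a less familiar test, a merging rule, and a repeat check of type I error once the site count is known.
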